7.3.2.2. Overall Response Rate

Overall response rate at Days 14, 56, and 100 is defined as the proportion of subjects demonstrating a CR, VGPR, or PR based on the MAGIC guidelines.

Subjects who have missing response data at Days 14, 56, and 100 (includes withdraw or death before these days) will be considered as nonresponders. The ORR on Days 14, 56, and 100 will be estimated with a 95% CI. The proportion of responders will be estimated with 95% CIs. Confidence intervals will be calculated based on the exact method for binomial distributions. Summary statistics will be provided.

7.3.2.3. Nonrelapse Mortality

Nonrelapse mortality is defined as the proportion of subjects who died due to causes other than malignancy relapse at Months 6, 9, 12, and 24.

Cumulative incidence functions of NRM will be estimated using Gray's method, and subjects with relapse-related mortality will be treated as competing risk and no observed mortality as censored at their last date known to be alive. Cumulative incidence rates of NRM at Months 6, 9, 12, and 24 will be estimated with 95% CI. Confidence intervals will be calculated based on the exact method for binomial distributions. Summary statistics will be provided.

7.3.2.4. Relapse Rate

Relapse rate is defined as the proportion of subjects whose underlying malignancy relapses. Primary disease relapse rate at Month 6 will be estimated with 95% CI. Confidence intervals will be calculated based on the exact method for binomial distributions. Cumulative incidence rate and summary statistics will be provided.

7.3.2.5. Relapse-Related Mortality Rate

Relapse-related mortality rate is defined as the proportion of subjects whose malignancy relapses and has a fatal outcome at Month 6. Relapse mortality rate will be provided with 95% CI. Confidence interval will be calculated based on the exact method for binomial distributions. Cumulative incidence rate and summary statistics will be provided.

7.3.2.6. Failure-Free Survival

Failure-free survival, defined as the proportion of subjects who are still alive, have not relapsed, have not required additional therapy for acute GVHD, and have not demonstrated signs or symptoms of chronic GVHD, at Month 6. The Kaplan-Meier method will be used to estimate the FFS time distribution and the median survival. Subjects with no observed death or loss to follow-up or have not relapsed, have not required additional therapy for acute GVHD, and have

not demonstrated signs or symptoms of chronic GVHD, at Month 6 will be treated as censored at Month 6. Survival rate at Month 6 will be estimated with 95% CI. The 95% CI will be calculated using the Brookmeyer and Crowley's method (Brookmeyer and Crowley 1982). Summary statistics will be provided.

7.3.2.7. Overall Survival

Overall survival is defined as the time from study enrollment (first date of ruxolitinib treatment) to death due to any cause. The Kaplan-Meier method will be used to estimate the survival time distribution and the median survival. Subjects with no observed death or loss to follow-up will be treated as censored at their last date known to be alive. Survival rate at Month 6 will be estimated with 95% CI. The 95% CI will be calculated using the Brookmeyer and Crowley's method (Brookmeyer and Crowley 1982). Summary statistics will be provided.

7.4. Pharmacokinetic Analyses

Noncompartmental analysis of the observed PK concentration data will be performed, and PK parameters, such as C_{max} , t_{max} , AUC, and $t_{\frac{1}{2}}$, will be generated and summarized wherever possible. Planned tables, listings, and figures are listed in Appendix B.

The population PK of ruxolitinib in subjects with myelofibrosis (MF) has been established in the previous MF New Drug Application. First, the PK data from this study will be applied to validate the final PK model established in the MF population. If significant biases are observed in this validation process, then a new population PK model may be generated based on the data from this study, and the model development process will follow the methods below. The data from this study may be combined with data from other clinical studies to improve parameter estimation.

The model development process consists of base pharmacokinetic model development and covariate analysis. In the base model development, compartment models with first-order absorption and linear elimination will be tested for their ability to characterize the PK of ruxolitinib in combination with corticosteroids for the treatment of steroid-refractory acute GVHD. Interindividual variability will be modeled using an exponential error model and explored for each PK parameter. Proportional, additive, and mixed error (additive plus proportional) models will be individually evaluated for their ability to describe the magnitude of residual variability. The first-order conditional estimation method with the interaction option will be used.

After a final base model is identified, covariates will be tested as predictors of PK variability. A generalized additive model analysis will be used as a screening tool to initially identify covariates to be formally tested for statistical significance in NONMEM. The candidate covariates will be incorporated into the PK model as fixed-effect parameters by making the typical values of the structural PK parameters a function of the covariate. NONMEM regression analysis will be performed on the model, with covariate parameters being added in a stepwise univariate fashion during the forward selection process and removed in the model reduction (backward elimination) process. The likelihood ratio test will be used to evaluate the significance of incorporating parameters into or removing parameters from the population model. The accuracy and robustness of the final population PK model will be investigated using a visual predictive check method.

The population PK data preparation will be performed using SAS v9.1 or later (SAS Institute Inc, Cary, NC).

The PK analyses will use NONMEM v7.1.0 or later (ICON Development Solutions, Dublin, Ireland).

8. SAFETY AND TOLERABILITY

8.1. General Considerations

The analyses for this section will be provided for the safety evaluable population. Summary tables may be replaced with listings when appropriate. For instance, an AE frequency table may be replaced with a listing if it only contains a few unique preferred terms reported on relatively few subjects.

8.2. Adverse Events

8.2.1. Adverse Event Definitions

A treatment-emergent adverse event (TEAE) is any AE either reported for the first time or the worsening of a pre-existing event after the first dose of study drug until 30 days after the last dose of study drug. Analysis of AEs (as discussed below) will be limited to TEAEs, but data listings will include all AEs regardless of their timing to study drug administration.

Adverse events will be tabulated by MedDRA preferred term and system organ class. Severity of AEs will be described and graded using the National Cancer Institute (NCI) CTCAE v4.03 (NCI 2010). The CTCAE reporting guidelines and grading details are available on the Cancer Therapy Evaluation Program website.

A grading (severity) scale is provided for each AE term. If the toxicity is not included in the CTCAE v4.03 criteria, then it will be rated on a scale of 1 to 4 as follows: 1 = mild, 2 = moderate, 3 = severe, and 4 = life-threatening. All toxicities will be graded based on the worst level reached, not the level they may have reached if they had not been treated. When the intensity of an AE changes over time for a reporting period (eg, between visits), then each change in intensity will be reported as an AE until the event resolves.

The subset of AEs considered by the investigator to be related to study drug will be considered to be treatment-related AEs. If the investigator does not specify the relationship of the AE to study drug, then the AE will be considered to be treatment-related. The incidence of AEs and treatment-related AEs will be tabulated. Serious AEs will also be tabulated.

Any missing onset date, causality, or severity must be queried for resolution. Unsolved missing values will be handled according to the following rules:

- An unsolved missing causality will be considered treatment-related.
- An unsolved missing severity will be identified as an unknown severity.

For purposes of analysis, all AEs will be considered TEAEs unless the AE can unequivocally be defined as not treatment-emergent.

8.2.2. Adverse Event Summaries

An overall summary of AEs will include the following:

- Number (%) of subjects reporting any TEAEs
- Number (%) of subjects reporting any SAEs
- Number (%) of subjects reporting any Grade 3 or 4 TEAEs
- Number (%) of subjects reporting any TEAEs related to ruxolitinib
- Number (%) of subjects reporting any TEAEs related to corticosteroids
- Number (%) of subjects who temporarily interrupted ruxolitinib because of a TEAE
- Number (%) of subjects with ruxolitinib dose reductions because of TEAEs
- Number (%) of subjects who permanently discontinued ruxolitinib because of a TEAE
- Number (%) of subjects who permanently discontinued ruxolitinib or corticosteroids because of a TEAE
- Number (%) of subjects who withdrew from the study because of a TEAE
- Number (%) of subjects who had a fatal TEAE
- Number (%) of subjects who had a TEAE of special interest

The following summaries will be produced by MedDRA term (if 10 or fewer subjects appear in a table, a listing may be appropriate):

- Number (%) of subjects reporting TEAEs by system organ class and preferred term
- Number (%) of subjects reporting TEAEs by preferred term in decreasing order of frequency
- Number (%) of subjects reporting TEAEs by system organ class, preferred term, and highest CTCAE grade
- Number (%) of subjects reporting any Grade 3 or 4 TEAEs by system organ class and preferred term
- Number (%) of subjects reporting treatment-related AEs by system organ class and preferred term
- Number (%) of subjects reporting treatment-related AEs by preferred term in decreasing order of frequency
- Number (%) of subjects reporting treatment-related AEs by system organ class, preferred term, and highest CTCAE grade
- Number (%) of subjects reporting fatal TEAEs by system organ class and preferred term
- Number (%) of subjects reporting treatment-emergent SAEs by system organ class and preferred term

- Number (%) of subjects reporting treatment-related SAEs by system organ class and preferred term
- Number (%) of subjects reporting TEAEs leading to dose reduction of ruxolitinib by system organ class and preferred term
- Number (%) of subjects reporting TEAEs leading to discontinuation of ruxolitinib by system organ class and preferred term
- Number (%) of subjects reporting treatment-emergent non-SAE by system organ class and preferred term

8.3. Clinical Laboratory Tests

8.3.1. Laboratory Value Definitions

Laboratory values and change from baseline values will be summarized descriptively by visit. The baseline value will be determined using the last nonmissing values collected before the first dose.

Laboratory test values outside the normal range will be assessed for severity based on CTCAE v4.03 grade or similar criteria where clinical intervention is required for CTCAE grading. The incidence of abnormal laboratory values and shift tables relative to baseline will be tabulated.

8.3.2. Laboratory Value Summaries

All test results and associated normal ranges from central laboratories will be reported in SI units. All tests with numeric values will have a unique unit per test. Any laboratory test results and associated normal ranges from local laboratories will be converted to SI units. For the limited number of cases where the associated normal ranges from a local laboratory cannot be obtained despite due diligence, associated central laboratory normal ranges will be applied. In the event that central laboratory normal ranges are not available, a set of standard normal ranges based on documented reference ranges will be applied to facilitate reporting the test results.

For numeric laboratory values, baseline value, postbaseline value, change from baseline, and percent change from baseline will be summarized by visit. In addition, mean change from baseline will be plotted over time for selected laboratory parameters.

Shift summaries will be presented showing the number and percentage of subjects with laboratory values of low, normal, and high at baseline along with change to the worst postbaseline visits. The denominator for the percentage calculation will use the number of subjects in the baseline category (ie, low, high, normal, missing).

For the laboratory parameters that have CTCAE grading, shift tables will also be presented showing change in CTCAE severity grade from baseline to worst grade postbaseline. Separate tables will be provided for selected laboratory tests that have grading criteria in both high and low directions. The denominator for the percentage calculation will be the number of subjects in the baseline category.

Categorical laboratory data will be tabulated by visit at baseline and postbaseline visits where appropriate.

8.4. Vital Signs

Values at each scheduled visit, change, and percentage change from baseline for vital signs, including systolic blood pressure, diastolic blood pressure, pulse, respiration rate, and body temperature, will be summarized descriptively.

Criteria for clinically notable vital sign abnormalities are defined in Table 1. The abnormal values for subjects exhibiting clinically notable vital sign abnormalities will be listed. Alert vital signs are defined as an absolute value outside the defined range and percentage change from baseline greater than 25%. The abnormal values for subjects exhibiting alert vital sign abnormalities will also be listed.

Parameter	High Threshold	Low Threshold
Systolic blood pressure	> 155 mmHg	< 85 mmHg
Diastolic blood pressure	> 100 mmHg	< 40 mmHg
Pulse	> 100 bpm	< 45 bpm
Temperature	> 38°C	< 35.5°C
Respiratory rate	> 24/min	< 8/min

 Table 1:
 Criteria for Clinically Notable Vital Sign Abnormalities

8.5. Electrocardiograms

Normal or abnormal 12-lead electrocardiograms (ECGs) will be collected and listed for each scheduled visit.

8.6. Analyses for the Data Monitoring Committee

No Data Monitoring Committee is planned.

9. INTERIM ANALYSES

An interim analysis will be conducted when 35 subjects complete the Day 28 visit. In this interim analysis, only futility will be assessed, and the study will be terminated if the lower boundary is crossed.

A group sequential design method for 1 sample binary outcome data will be used to calculate the lower boundary of futility. The spending function of HSD(-4) will be used. For H0: p = 0.4, Ha: p = 0.6, and a 1-sided binomial test with alpha of 0.025, if ≤ 15 subjects respond at the time of the interim analysis, the study will be terminated. This will provide 70.03% probability for the response rate of 40% at the interim analysis.

If \geq 37 subjects respond at the time of final analysis, the study outcome will be considered positive. These assumptions will provide 89.88% power for the response rate of 60% in the final analysis with Type I error of 0.0189.

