9.2. Selection of Sample Size

Approximately 70 subjects are planned for the final analysis of the primary endpoint of ORR. A treatment regimen for steroid-refractory GVHD demonstrating an absolute improvement of 20% versus historic data would be considered clinically meaningful. With the assumed true rate of 60%, a sample size of 70 subjects would provide > 90% probability to have a 95% CI with lower limit of \geq 40%.

An interim analysis will be conducted when 35 subjects complete the Day 28 visit in order to assess for futility; if the lower boundary is crossed, the study will be terminated.

A group sequential design method for 1 sample binary outcome data will be used to calculate the lower boundary of futility. The spending function of HSD(-4) will be used. For H0: p = 0.4, Ha: p = 0.6, and a 1-sided binomial test with alpha of 0.025, if ≤ 15 subjects respond at the time of the interim analysis, the study will be terminated. This will provide 70.03% probability for the response rate of 40% at the interim analysis.

If \geq 37 subjects respond at the time of final analysis, the study outcome will be considered positive. These assumptions will provide 89.88% power for the response rate of 60% in the final analysis with Type I error of 0.0189.

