9.4. Statistical Analyses

9.4.1. Primary Analyses

The primary endpoint is ORR at Day 28, defined as the proportion of subjects demonstrating a CR, VGPR, or PR, as per standard criteria (Appendix B). The primary analysis will be conducted once the last subject completes the Day 28 visit or withdraws from the study.

Summary statistics and 95% CI will be provided.

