9.6. Interim Analysis

An interim analysis will be conducted when 35 subjects complete Day 28 visit. In this interim analysis, only futility will be assessed, and the study will be terminated if the lower boundary is crossed.

A group sequential design method for 1 sample binary outcome data will be used to calculate the lower boundary of futility. The spending function of HSD(-4) will be used. For H0: p = 0.4, Ha: p = 0.6, and a 1-sided binomial test with alpha of 0.025, if ≤ 15 subjects respond at the time of the interim analysis, the study will be terminated. This will provide 70.03% probability for the response rate of 40% at the interim analysis.

If \geq 37 subjects respond at the time of final analysis, the study outcome will be considered positive. These assumptions will provide 89.88% power for the response rate of 60% in the final analysis with Type I error of 0.0189.

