7.3. Analyses of the Efficacy Parameters

7.3.1. Primary Efficacy Analysis

Overall response rate at Day 28 is defined as the proportion of subjects demonstrating a CR, VGPR, or PR as per standard criteria (see Appendix B).

The proportion of responders will be estimated with 95% CIs for the efficacy evaluable population. Confidence intervals will be calculated based on the exact method for binomial distributions. Summary statistics will be provided.

Subjects who have missing response data at Day 28 (includes withdrawal or death before Day 28) will be considered nonresponders. The primary analysis will be conducted when all subjects have completed Day 28 response assessments or discontinued.

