7.3.2. Secondary and Efficacy Analysis

7.3.2.1. Duration of Response

Duration of response at Month 6 is the key secondary endpoint. For responders, the DOR is defined as the difference of the end of response and the start of response for subjects who have at least 1 response measurement. The start of a response will be the first visit where the subject achieves PR or better based on response criteria in Appendix B (MAGIC guidelines). The end of response will be the first visit after GVHD progression based on response criteria in Appendix B or death. Duration of response will be assessed using the Kaplan-Meier method for subjects who achieve a response. Median duration and 95% CI will be estimated. Subjects who are still responding at the time of database lock or discontinuation will be right-censored at the

time of last valid response assessment. Six-month DOR will be assessed when all subjects complete the Day 180 visit.

In addition, 3-month DOR will be assessed. Three-month DOR is defined as the time from first response until GVHD progression or death, when all subjects complete the Day 84 visit. Duration of response will be assessed using the Kaplan-Meier method for subjects who achieve a response.

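### The success threshold is a fixed 37 responders although enrollment is only approximately 70, so the stated type I error and power hold only at exactly 70 subjects

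*SAP*

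**What the plan says.** **Final decision.** Protocol 9.2 and 9.6 and SAP 3.2 and 9 all give the same rule. The null rate is 0.4, the alternative 0.6, and the test is one-sided at 0.025. The outcome is positive with 37 or more responders, with stated power of 89.88% and type I error of 0.0189. The rule names a number of responders and no denominator.

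**Number of subjects.** Protocol 4.3.1 and SAP 3.2 put the sample at approximately 70. SAP 5.3.1 places all enrolled subjects in the efficacy evaluable population, and SAP 7 uses that population for every efficacy analysis. Protocol 4.3.2 makes no provision for replacing subjects. SAP 7.3.1 reports the Day 28 response rate with an exact 95% interval. SAP 3.2 also says that, at a true rate of 60%, 70 subjects give more than 90% probability that the lower limit is at least 40%.

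**Interim.** The study stops if 15 or fewer subjects respond. SAP 9 states the timing as "An interim analysis will be conducted when 35 subjects complete the Day 28 visit", and Protocol 9.2 agrees: "An interim analysis will be conducted when 35 subjects complete the Day 28 visit in order to assess for futility". Of the boundary, Protocol 9.6 says: "This will provide 70.03% probability for the response rate of 40% at the interim analysis".

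**Primary analysis timing.** SAP 7.3.1 sets it "when all subjects have completed Day 28 response assessments or discontinued", and Protocol 9.4.1 "once the last subject completes the Day 28 visit or withdraws from the study". SAP 7.3.1 adds: "Subjects who have missing response data at Day 28 (includes withdrawal or death before Day 28) will be considered nonresponders".

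**The concern.** A fixed count is a different hurdle at each sample size. Thirty-seven of 70 is 52.9%, 37 of 72 is 51.4%, and 37 of 68 is 54.4%. Since approximately 70 permits a final number slightly above or below 70, and all enrolled subjects are analysed, the false-positive risk and the power depend on where enrollment happens to end. Two subjects over target would be enough for the plan to exceed its own alpha. Two under would make it call a result negative when the reported interval lies wholly above 40%.

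There is a smaller question at the interim. The primary analysis says what happens to subjects who die or leave before Day 28; the interim trigger does not. A reader could count such subjects among the 35 as nonresponders, or wait for 35 who actually attend the visit.

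**Working it through.** **Inputs from the documents:** interim n = 35, stop at 15 or fewer; final N = 70, success at 37 or more; p0 = 0.4, p1 = 0.6; one-sided alpha 0.025.

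**1. Reproduce the plan's figures (exact binomial).**
- Probability of stopping at 40%: P(X ≤ 15 | n = 35, p = 0.4) = 0.7003, which matches 70.03%.
- Probability of a positive outcome: sum over x = 16 to 35 of P(X1 = x | 35, p) × P(X2 ≥ 37 − x | N − 35, p), with N = 70. This gives 0.0189 at p = 0.4 and 0.8988 at p = 0.6, matching the stated type I error and power.
- Without the futility look, P(X ≥ 37 | 70, p) is 0.0199 at 0.4 and 0.9094 at 0.6. The second figure agrees with the statement of more than 90% probability in SAP 3.2.

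So every stated figure is correct for exactly 35 and 70.

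**2. Keep 37 and the futility rule; vary the final N.** The same formula is used, with the exact (Clopper-Pearson) lower limit for 37 responders alongside.

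| N | Type I error | Power | Lower limit for 37/N |
|---|---|---|---|
| 68 | 0.0110 | 85.0% | 41.9% |
| 69 | 0.0145 | 87.7% | 41.2% |
| 70 | 0.0189 | 89.9% | 40.6% |
| 71 | 0.0241 | 91.6% | 39.9% |
| 72 | 0.0303 | 93.0% | 39.3% |
| 73 | 0.0374 | 94.1% | 38.7% |

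Type I error first passes 0.025 at N = 72. At N = 71 it is still below 0.025, but the lower limit for 37 responders has dropped under 40%. At N = 68, 36 responders miss the count although the lower limit for 36/68 is 40.45%.

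**3. Replace the count by an exact lower limit of at least 40% at the actual N.**

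| N | Responders needed | Lower limit | Type I error | Power |
|---|---|---|---|---|
| 68 | 36 | 40.45% | 0.0199 | 89.5% |
| 69 | 37 | 41.2% | 0.0145 | 87.7% |
| 70 | 37 | 40.6% | 0.0189 | 89.9% |
| 71 | 38 | 41.3% | 0.0139 | 88.2% |
| 72 | 38 | 40.65% | 0.0180 | 90.3% |
| 73 | 38 | 40.04% | 0.0229 | 91.9% |

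The bound is general. An exact two-sided 95% lower limit of at least 40% requires P(X ≥ r | N, 0.4) ≤ 0.025, and a futility stop can only lower the chance of a positive result.

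**4. Interim trigger.** Suppose only subjects who attend Day 28 count toward the 35, and 40% is the rate over all enrolled. With a fraction d lost before Day 28, the stopping probability is P(X ≤ 15 | 35, 0.4/(1 − d)). The documents give no value for d, so these are assumptions: 68.3% at d = 1%, 60.6% at 5% and 49.5% at 10%. With N = 70, allowing for the losses that accrue before the 35th completer, type I error is 0.0190, 0.0194 and 0.0197 and power is 90.1%, 90.7% and 90.9%. Neither can exceed the values without a futility look, 0.0199 and 90.94%.

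**The case against.** **On the success count.** The 37 belongs to a design for 70, and nothing in the documents forecasts 72 or more. Both documents say that no formal tests will be done (Protocol 9.3, SAP 3.1 and 7.2), and the exact interval is reported whatever N turns out to be, so 37 of 72 would visibly show a lower limit of 39.3%. The 40% lower limit in SAP 3.2 describes what 70 subjects would achieve; it is not written as a criterion.

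Much of this stands. The harm depends on the final N, and a reader who infers that the plan breaks a success criterion of its own reads too much into SAP 3.2: using the 40% limit for the decision would be a new choice. But the plan states an alpha, a type I error and a threshold for a positive outcome. That is a decision rule, and approximately 70 lets it be applied at sizes where its stated properties fail. The disclaimer on testing does not remove this.

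**On the interim trigger.** A reader might infer that 70.03% is wrong, or that the interim and primary analyses conflict. The documents do not support that. SAP 7 applies the all-enrolled population to every efficacy analysis, the planned interim response table (Table 2.1.3 in SAP Appendix A) names the efficacy population, and SAP 7.3.1 counts missing responses as nonresponse. The documents also use the word complete loosely elsewhere: "Six-month DOR will be assessed when all subjects complete the Day 180 visit" cannot mean that no subject dies before Day 180. The natural meaning of the 40% is the rate among those analysed at the look, and then 70.03% is correct under either trigger. The shortfall in step 4 needs a literal trigger, an all-enrolled 40% and an assumed loss rate together.

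What remains is that the text does not say outright which 35 subjects form the interim cohort. The study is open-label and SAP 8.6 says "No Data Monitoring Committee is planned", so it is better settled in writing than at the time of the look.

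**Conclusion.** The concern holds for the success threshold and should be fixed. The stated 0.0189 and 89.88% are right at exactly 70 subjects. With 37 fixed, type I error passes one-sided 0.025 from 72 subjects (0.0303, then 0.0374 at 73), while at 68 power falls to 85.0%. At 71, type I error is 0.0241, within the limit. If enrollment ends at 69 or 70, the count and a 40% lower limit give the same decision. These figures assume the futility rule as stated, with 35 subjects at the look and all enrolled subjects in the final denominator; they need no loss rate.

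The interim trigger is a minor clarification and not an error. The likely intent can be recovered from the SAP. The other reading would only weaken the futility stop; at 70 subjects it does not raise type I error above 0.0199 or reduce power.

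**What to change.** **Success rule (SAP 3.2 and 9, Protocol 9.2 and 9.6).** Replace the bare count with: the outcome is positive if the lower limit of the exact 95% confidence interval for Day 28 response is at least 40% at the actual number enrolled. Give the counts: 36 at 68 subjects, 37 at 69 or 70, 38 at 71 to 73. State openly that this turns what is now a sample-size property into the decision rule. It uses the interval that SAP 7.3.1 already computes and adds no subjects or visits.

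The cost is power above 70, compared with the fixed count: 88.2% rather than 91.6% at 71, 90.3% rather than 93.0% at 72, and 91.9% rather than 94.1% at 73. At 68, power rises from 85.0% to 89.5%. A hard cap at 70 would also prevent the overshoot, but would leave the rule undefined if enrollment falls short.

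**Interim trigger (same sections).** Add that the look is made when the first 35 enrolled subjects have each completed the Day 28 assessment or discontinued (including by death), with a missing response counted as nonresponse. Keep the boundary at 15. The stated 70.03% then holds at any early-loss rate. Compared with waiting for any 35 completers, the look may come slightly later for a subject whose visit is delayed for safety reasons (Protocol 6.2) or whose first dose follows enrollment by up to 2 days (Protocol 6.1).
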